**Table 1 - Definition of the patient status regarding hepatitis C virus**

	Hepatitis C Antibody (Ab) test result				
	Negative		Positive		
Reflexive test a – hepatitis C RNA test	Not available or HCV RNA not detected	HCV RNA detected	HCV RNA not detected b	HCV RNA detected	Not available
Hepatitis C status - label	Negative	Positive RNA	Negative b	Positive RNA	Positive Ab – no RNA available

*a* Test performed at the same time or after the antibody test in the pre-treatment period (for baseline evaluation), or post-baseline, respectively

*b* For post-baseline evaluation, a second antibody test with a different type of assay is to be done at the same date or after the first antibody test. The result of this test will modify the final hepatitis C status of the patient in some cases (see details in the text below the table)

The baseline evaluation will be based on tests performed during the pre-treatment period.

In case of multiple hepatitis C tests available for the post-baseline evaluation, the positive status of the patient will be defined as follows:

- “Positive” status if at least one post-baseline positive RNA is detected, regardless of status of the patient at the end of treatment.
- Else “Positive Ab – no RNA available” status if no post-baseline reflexive RNA test is available for at least one post-baseline positive antibody test.

If no antibody test is available or with “indeterminate” as result pre-treatment or post-baseline, respectively, the RNA test (if available) will be used alone to determine the status of the patient. If no RNA is available then the hepatitis C status of the patient will be missing.

The post-baseline status “confirmed positive antibody with negative RNA” will replace “Negative” status as defined above in the case where no RNA was detected post-baseline and the 2 antibody tests surrounding the same visit (from 2 different types of assay) are positive.

For a conservative approach, the post-baseline status “Positive Ab – no RNA available” will not be modified by the availability of a second antibody test from a different assay.

For the description of the positive hepatitis C virus test during the TEAE period, all above rules applied by replacing post-baseline by TEAE period.

### ***Drug-induced liver injury***

The liver function tests, namely AST, ALT, alkaline phosphatase (ALP), and total bilirubin, are used to assess possible drug-induced liver toxicity. The proportion of patients with PCSA values or ALT increase as defined in AESI section (see [Section 2.1.4.1](#)) during TEAE period by baseline status will be displayed by treatment group for each parameter.

An evaluation of drug-induced serious hepatotoxicity (eDISH) with the graph of distribution of peak values of ALT versus peak values of total bilirubin will also be presented using post-baseline values during TEAE period. Note that the ALT and total bilirubin values are presented on a logarithmic scale. The graph will be divided into 4 quadrants with a vertical line corresponding to 3 x ULN for ALT and a horizontal line corresponding to 2 x ULN for total bilirubin.

Listing of possible Hy's law cases identified by treatment group (ie, patients with any elevated ALT>3 x ULN, and associated with an increase in bilirubin >2 x ULN, concomitantly or not) with ALT, AST, ALP, total bilirubin, and if available, direct and indirect bilirubin will be provided.

The incidence of liver-related TEAEs will be summarized by treatment group. The selection of PTs will be based on SMQ Hepatic disorder (see [Section 2.4.5.1](#)).

#### ***2.4.5.4 Analyses of vital sign variables***

The summary statistics (including number, mean, median, Q1, Q3, standard deviation, minimum and maximum) of all vital signs variables in sitting position (central laboratory values and changes from baseline) will be calculated for each visit or study assessment (baseline, each post-baseline time point, last on-treatment, worst on-treatment value, and follow-up visit) by treatment group. In addition for some parameters of interest; mean changes from baseline with the corresponding SE could be plotted over time (at same time points) in each treatment group.

Vital signs without position filled in will only be used for the PCSA analysis described below.

The incidence of PCSAs at any time during the treatment-emergent adverse event period will be summarized by treatment group irrespective of the baseline level and/or according to the following baseline status categories:

- Normal/missing;
- Abnormal according to PCSA criterion or criteria.

If any clinically significant signal is detected and needs further characterization, exploration of time to onset will be performed for selected PCSAs assessed during the TEAE period as described below to account for the differential exposure time in all patients.

Kaplan-Meier curves during TEAE period will be also provided using the midpoint of the time interval between the first assessment with PCSA and the previous assessment. Only the first event

(PCSA) will be counted. Patients without any event will be censored at the last assessment performed during the TEAE period.

#### **2.4.5.5 Analyses of electrocardiogram variables**

The count and percentage of patients with at least 1 abnormal ECG will be summarized by treatment group during TEAE period according to the following baseline status categories:

- Normal/missing;
- Abnormal.

#### **2.4.6 Analyses of other endpoints**

All analyses for other endpoints will be performed on the Safety population. All measurements, scheduled or unscheduled, fasting or not fasting, will be assigned to analysis windows defined in [Section 2.5.4, Table 2](#) in order to provide an assessment for Week 4 to Week 24 time points.

HbA1c parameter will be summarized by analysis visit using number of available data, mean, SD, median, minimum, and maximum for each treatment group during the treatment period. Summary will also be provided according to the diabetes mellitus status at baseline. The time profile will also be plotted by treatment group with the means and the corresponding SEs. The incidence of PCSA at any time during the TEAE period will also be summarized by treatment group using descriptive statistics, overall and according to diabetes mellitus status at baseline.

Binary endpoints defined in [Section 2.1.5](#) will be described using count and percentage. Kaplan-Meier curves will be provided for the “Time to” variables. Patient without event will be censored at the end of the treatment period. For the analysis of the time to the first of the 2 consecutive LDL-C, patients without post-baseline LDL-C result or with only 1 post-baseline LDL-C result will not be included.

#### **2.4.7 Analyses of anti-alirocumab antibodies variables**

The following summaries will be performed on the ADA population, taking into account all samples regardless of timing relative to the injections:

- ADA results (negative or positive) by time point and by treatment group and also according to up-titration status;
- Neutralizing status (negative or positive) by time point for positive ADA and by treatment group and also according to up-titration status;
- ADA titers using descriptive statistics (median, minimum and maximum) for positive ADA by time point and by treatment group and also according to up-titration status;
- Number (%) of patients with pre-existing ADA and number (%) of patients with treatment-emergent ADA positive response by treatment group, overall and according to up-titration status;
- Number (%) of patients with persistent/transient/indeterminate treatment-emergent ADA positive response by treatment group, overall and according to up-titration status;

- Time to onset of treatment-emergent ADA positive response using descriptive statistics by treatment group, overall and according to up-titration status.

Correlations between ADA parameters (eg, titers, treatment-emergent ADA positive status, neutralizing status) and safety and/or efficacy endpoints will be also explored (eg, scatter plot).

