10.6.2.1 Allergic adverse events with cutaneous involvement

AEs with cutaneous involvement which are obviously of allergic origin, general allergic reactions or local injection site reactions (with an allergic component) which progress/expand/worsen/etc should be evaluated by a dermatologist as soon as possible, and preferably within one week of the site first becoming aware of the event.

The investigator should evaluate the patient for possible etiologies (new medications, etc) and extra-cutaneous symptoms and signs. An unscheduled Central Laboratory assessment for

hematology, chemistry, liver panel and ADA should be obtained. If it is possible, the site will take pictures of the skin lesions in order to provide the patient with them for the dermatologist's visit. If the photos are obtained, then copies should be kept as source documents which may later be collected by the sponsor. The investigator will provide a summary of the patient's case, reason for consultation, and information being requested to the consulting dermatologist.

A full consultation report should be sent by the dermatologist to the investigator. The full report should contain, at a minimum, the following information; a detailed description of the rash (such as the morphology [lesion type], shape of individual lesions, arrangement of multiple lesions [eg, scattered, grouped, linear], distribution, color, consistency, presence of pruritus or pain, and other clinical signs) and in case a skin biopsy (including histopathology and immunofluorescence) was done (if it was deemed necessary as per the dermatologist's or investigator's medical judgment), the results of this investigation with, if applicable, a specific diagnosis of the AE. The investigator will fax the full report and the corrected AE form if necessary, to the Monitoring Team Representative within 24 hours.

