## 2.1.6 Anti-alirocumab antibodies variables

Anti-alirocumab antibodies are assessed at baseline (before the first IMP injection), at Week 4, Week 12, Week 24/or early termination and during follow-up (Week 32). Anti-drug antibody (ADA) measurements will be assigned to similar analysis windows as defined for efficacy endpoints ([Table 2](#)), with an additional analysis window for the ADA follow-up measurement performed at Week 32.

The following variables will be described:

- ADA response (Positive or Negative). For ADA positive
  - Titer levels;
  - Neutralizing status (Positive or Negative).
- Pre-existing positive ADA defined as patients with positive ADA response at baseline with less than 4-fold increase in titer in the post-baseline period;
- Treatment-emergent positive ADA response defined as 1) Patients with no ADA positive response at baseline but with any positive response in the post-baseline period (up to follow-up visit) or 2) Patients with a positive ADA response at baseline and at least a 4-fold increase in titer in the post-baseline period (up to follow-up visit). For treatment-emergent positive ADA, the following categories for ADA duration will be applied:
  - A persistent positive response is a treatment-emergent ADA positive response detected in at least 2 consecutive post-baseline samples separated by at least a 12-week period;
  - An indeterminate duration positive response is defined as ADA present only at the last sampling time point;
  - A transient positive response is defined as any treatment-emergent positive ADA response that is neither considered persistent nor indeterminate.

In addition, potential ADA samples to be collected after follow-up visit for patients with titer >240 at early end of treatment or follow-up visit will be listed.

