#### 2.5.5 Unscheduled visits

For efficacy, safety laboratory data, and vital signs, unscheduled visit measurements may be used to provide a measurement for a time point, a baseline, a last or a worst value, if appropriate according to their definitions. The measurements may also be used to determine abnormal/PCSA.

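### An antibody sample triggered by a cutaneous allergic event can count toward treatment-emergent ADA, so the exploratory association of ADA with those events may be modestly inflated

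*SAP*

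**What the plan says.** - **Schedule.** SAP 2.1.6 has ADA assessed at baseline and then "at Week 4, Week 12, Week 24/or early termination and during follow-up (Week 32"). That is four planned post-baseline samples per patient.
- **Triggered sample.** Protocol 10.6.2.1 covers "AEs with cutaneous involvement which are obviously of allergic origin, general allergic reactions or local injection site reactions (with an allergic component") that spread or get worse. For these it asks for an unscheduled central-laboratory assessment: "hematology, chemistry, liver panel and ADA should be obtained".
- **Definition.** Under SAP 2.1.6, treatment-emergent positives include "Patients with no ADA positive response at baseline but with any positive response in the post-baseline period (up to follow-up visit"). The definition is not confined to scheduled samples.
- **Summaries.** SAP 2.4.7 analyses the ADA population "taking into account all samples regardless of timing relative to the injections".
- **Exploration.** The same section adds: "Correlations between ADA parameters (eg, titers, treatment-emergent ADA positive status, neutralizing status) and safety and/or efficacy endpoints will be also explored (eg, scatter plot").
- **Windows.** SAP 2.1.6 says ADA values "will be assigned to similar analysis windows as defined for efficacy endpoints". Under SAP 2.5.4, one value is kept per window, the one nearest the target day.
- **Unscheduled visits.** SAP 2.5.5 reads: "For efficacy, safety laboratory data, and vital signs, unscheduled visit measurements may be used to provide a measurement for a time point". ADA is not in that list.

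**The concern.** Whether a patient has the fifth sample depends on whether the patient had the allergic event. Under an any-positive rule, an added sample can raise the chance of being classed positive or leave it unchanged; it cannot lower it. If treatment-emergent ADA is then compared between patients with and without these events, the event group has had more looks. Some positive association would be expected even if antibodies and allergy were unrelated.

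This is a comparison that readers will look for. Protocol section 4, in its benefit-risk conclusion, names immunogenicity and hypersensitivity reactions among the important identified or potential risks. A plot or table of ADA status against allergic events does not show that the groups were sampled unequally, and neither document excludes the triggered sample or allows for the number of samples taken.

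**Working it through.** The documents give no ADA incidence and no figure for the effect of unscheduled sampling, so there is no stated figure to reproduce. The check has two parts.

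**1. Does the triggered sample count?**

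Taken literally, SAP 2.1.6 (any positive) and 2.4.7 (all samples) let it count. The window rule does not reliably remove it, even if it is applied to treatment-emergent status. The Week 8 window (Days 43 to 70) and the Week 16 window (Days 99 to 126) contain no scheduled ADA sample, so a triggered sample there would normally be the only value and be kept. In the other windows it is kept if it lies nearest the target day, but then it replaces the scheduled value and adds no extra look.

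**2. How large could the effect be?**

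Inputs:
- Four scheduled samples (SAP 2.1.6) against five with one triggered sample (Protocol 10.6.2.1).
- Per-sample positivity p from 0.5% to 10%, and within-patient correlation ρ from 0 to 0.9. Both are assumed.
- No true association, and a triggered sample as likely to be positive as a scheduled one. Both are assumed.

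For independent samples, P(any positive in m) = 1 − (1 − p)^m.

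| p | 4 samples | 5 samples | Risk ratio | Odds ratio |
|---|---|---|---|---|
| 0.5% | 2.0% | 2.5% | 1.247 | 1.253 |
| 1% | 3.9% | 4.9% | 1.244 | 1.256 |
| 2% | 7.8% | 9.6% | 1.238 | 1.263 |
| 5% | 18.6% | 22.6% | 1.220 | 1.284 |
| 10% | 34.4% | 41.0% | 1.191 | 1.323 |

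For example, at p = 1%: 1 − 0.99^4 = 0.0394, 1 − 0.99^5 = 0.0490, and 0.0490 / 0.0394 = 1.244. As p approaches zero the risk ratio approaches 5/4 = 1.25, which is its ceiling. The odds ratio can exceed that.

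For correlated samples a beta-binomial model gives P(any positive in m) = 1 − B(a, b + m) / B(a, b), with a = p(1 − ρ)/ρ and b = (1 − p)(1 − ρ)/ρ. Over the same range of p, the risk ratio for 5 against 4 samples is:

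| ρ | Risk ratio |
|---|---|
| 0 | 1.19 to 1.25 |
| 0.3 | 1.12 to 1.14 |
| 0.6 | 1.07 to 1.08 |
| 0.9 | about 1.02 |

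**Absolute size.** Take 400 alirocumab patients (Protocol 11.1), with 8 to 40 of them assumed to have a triggering event, and independent samples. The extra sample adds between 8 × (0.0248 − 0.0199) = 0.04 and 40 × (0.4095 − 0.3439) = 2.6 expected positives. The spurious phi correlation is 0.005 to 0.041.

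**A second source of extra samples.** Under Protocol 10.3.4, early discontinuers have an unscheduled visit with end-of-treatment assessments, which include ADA (Protocol 10.1.2.5), and then resume the schedule. A patient with both kinds of extra sample has 6 against 4, with a ceiling of 6/4 = 1.50.

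**With scheduled samples only.** Everyone has the same four planned looks, so under no true association the expected risk ratio is 1.00.

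**The case against.** The strongest reply is that the SAP never says unscheduled ADA samples are used. The qualifier in SAP 2.4.7 concerns timing against injections. Elsewhere the SAP states outright that unscheduled values are included (for example 2.1.3 and 2.4.5), while 2.5.5 leaves ADA out. This stands in part. Inclusion is implied by the any-positive definition and the all-samples wording, not stated. But no passage excludes these samples either, so a programmer following the text would count them.

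The second reply is that five against four is not general. If windows govern status, a triggered sample adds a look mainly in the Week 8 and Week 16 windows (28 + 28 = 56 days) or where a scheduled sample is missing. Elsewhere it replaces a scheduled value, or falls in no window, as on Days 1 to 14 or 127 to 154. This stands as a further reason to expect a smaller effect. The SAP does not say that windows govern treatment-emergent status.

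Third, the analysis is exploratory and graphical, and SAP 2.4.5 plans no formal inferential testing of safety data. That is correct and limits the consequence. It does not remove the bias from the display.

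Fourth, a scheduled-only analysis discards the sample drawn at the reaction, which may be the most informative about an antibody-related event. That is a fair objection to replacing the all-samples version, but not to showing both.

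Fifth, suspected allergy to study drug leads to interruption of treatment (Protocol 10.6.2), so later exposure also differs between the groups. The sampling component pushes upward, but the net direction of the observed association is not settled by sampling alone.

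**Conclusion.** The point holds in a limited form. The protocol adds an ADA sample because of a cutaneous allergic event. The SAP as written lets that sample count toward treatment-emergent ADA, and nothing equalises the sampling. The exploratory association of treatment-emergent ADA with those events, and with endpoints overlapping them, may therefore be modestly inflated. For one extra sample the spurious risk ratio is at most 1.25, and nearer 1.02 to 1.08 when within-patient correlation is 0.6 to 0.9. These sizes rest on assumed positivity and correlation, and on the triggered sample being no more likely to be positive than a scheduled one.

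A reader might infer three stronger things that the documents do not support:
- **That the whole ADA-versus-safety exploration is inflated.** Efficacy endpoints and unrelated safety endpoints do not trigger this sample.
- **That a ratio of 1.22 to 1.24 is the expected size.** It requires independent samples and positivity of 1% to 5%, neither of which is in the documents.
- **That every ADA measure moves upward.** Persistence can move the other way. Positives at Weeks 12 and 24 are consecutive and 12 weeks apart, so they meet the SAP 2.1.6 rule. A positive sample inserted at Week 18 leaves two 6-week gaps, and on a literal reading the patient no longer qualifies.

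No primary or key secondary conclusion depends on this.

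**What to change.** In SAP 2.4.7:
- Flag unscheduled ADA samples, separating those triggered by an event from extra samples at early end-of-treatment visits.
- Present treatment-emergent ADA incidence, and its comparison with allergic events, from scheduled samples only (Weeks 0, 4, 12, 24 and 32) beside the all-samples version.
- List triggered samples with the event that prompted them.

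The same wording should say which samples feed the persistence categories, since SAP 2.5.5 does not mention ADA.

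The cost is one flag, one extra display and a few lines of SAP text, with no change to data collection. The downside is that the scheduled-only version misses a transient positive seen only at the reaction. That result stays in the all-samples version and in the listing.

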##### ***Titration***

The number and percentage of patients with an up-titration in the alirocumab group will be described. Patients with an up-titration are defined as up-titrated patients according to IVRS/IWRS Week 12 transaction with at least 1 injection of alirocumab 150 mg afterwards.

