- For exploratory purpose, key safety analyses could also be provided according to up-titration status, ie, according to whether the patients remained on the 75 mg dose or whether they were up-titrated to 150 mg. These analyses will be exploratory and descriptive (no formal comparison per dose) as it is expected that there could be inherent differences in the baseline characteristics between those patients titrating to 150 mg and those remaining on 75 mg. In order to reduce the bias of this analysis, the period before the up-titration time point (planned at Week 12) will be analyzed separately since only the dose 75 mg is proposed for this time period and consequently the early events occurring before Week 12 can only be attributed to this dose. Therefore the descriptive analysis per dose will include any safety events occurring from the first injection post Week 12 IVRS/IWRS transaction to the end of the TEAE period. Baseline characteristics of patients receiving each dose will be summarized.

Analyses performed according to diabetes status will be done considering diabetic patients as patients with either type 1 or type 2 diabetes in the medical history e-CRF page (regardless of the ongoing status).

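### Treatment-emergent ADA incidence, persistence and onset are split by up-titration status with no Week 12 cut, so responses that predate any 150 mg injection enter the comparison

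*SAP*

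**What the plan says.** SAP 2.4.7 lists six ADA summaries. Three of them (ADA result, neutralizing status, titer) are given by time point as well as by up-titration status. The other three are patient-level: incidence, persistence class and time to onset of treatment-emergent ADA. The incidence and persistence items are given for "treatment-emergent ADA positive response by treatment group, overall and according to up-titration" status, and the onset item is split likewise. The section works from the ADA population, "taking into account all samples regardless of timing relative to the injections", and sets no cut at Week 12.

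Under SAP 2.1.6, a patient negative at baseline becomes treatment-emergent positive on any later positive sample through the follow-up visit. Scheduled post-baseline samples fall at Weeks 4, 12, 24 and 32.

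SAP 2.4.3.1 (Titration) counts as up-titrated the "up-titrated patients according to IVRS/IWRS Week 12 transaction with at least 1 injection of alirocumab 150 mg afterwards". For safety analyses by the same status, the general common rules in SAP 2.4.5 say that "the period before the up-titration time point (planned at Week 12) will be analyzed separately", with the stated aim of reducing bias. The per-dose description then starts at the first injection after the Week 12 transaction. SAP 2.4.7 neither repeats that rule nor refers to it.

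**The concern.** Up-titration status does not exist until Week 12, yet the three patient-level tables use it to classify responses that may have been detected at Week 4 or Week 12. At those samples every alirocumab patient had received only 75 mg. A patient first positive at Week 4 and later up-titrated is counted in the up-titrated row, with an onset time that predates the higher dose.

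The classification may also depend on the outcome. Up-titration follows from Week 8 LDL-C of 70 mg/dL or more. If an early antibody weakens the LDL-C response, it makes up-titration more likely, and antibodies then collect in the up-titrated row for a reason that runs from antibody to dose.

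Antibody development is a stated secondary objective (Protocol 5.2, SAP 1.2.2), so these rows will be read. A reader who sees more ADA, or a different onset pattern, among up-titrated patients could not tell from these tables how much of it arose before 150 mg was given.

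**Working it through.** The plan states no figure to reproduce here. The check is a comparison of texts, a count of samples, and an illustration with assumed rates.

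**Which samples precede 150 mg**

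- Dose: Protocol 8.5 has all alirocumab patients on 75 mg until the Week 12 visit.
- Timing within a visit: the Protocol 1.2 flow chart notes put ADA sampling before the injection.
- Analysis window: SAP 2.5.4, Table 2 closes the Week 12 window no later than the first injection from the kit allocated at the up-titration contact.
- Result: the Week 4 and Week 12 samples, 2 of 4 scheduled post-baseline samples, precede any 150 mg injection.

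**Persistence class**

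SAP 2.1.6 requires consecutive positive samples at least 12 weeks (84 days) apart. Week 24 is Day 169 ± 3 and Week 32 is Day 225 ± 7 (Protocol 1.2).

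- Planned gap: 225 − 169 = 56 days.
- Largest gap within the visit windows: 232 − 166 = 66 days, below 84.

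So on planned visits a response first detected at Week 24 cannot be classed as persistent. Every persistent response in the up-titrated column must have been first detected at Week 4 or Week 12. Only off-window or unscheduled samples could be exceptions.

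**Illustration (assumed rates, no dose effect)**

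N = 400 alirocumab patients (SAP 1.1). Assumed and not in the documents:

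- u, the fraction up-titrated;
- e, the fraction with treatment-emergent ADA first detected by Week 12;
- l, the fraction of the rest with later onset, equal in both status groups;
- r, how many times likelier up-titration is after early ADA.

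The chance of up-titration without early ADA is a = u / [(1 − e) + e·r]. Early cases in the up-titrated row number N·e·r·a. Late cases are l times the patients in that row without early ADA.

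With u = 20%, e = 3%, l = 2%, r = 2:

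- a = 0.20 / (0.97 + 0.06) = 0.194.
- Early cases: 12 × 2 × 0.194 = 4.66 up-titrated, 12 − 4.66 = 7.34 others.
- Late cases: (80 − 4.66) × 0.02 = 1.51 and (320 − 7.34) × 0.02 = 6.25.
- Unsplit incidence: 6.17/80 = 7.71% against 13.59/320 = 4.25%, ratio 1.81.
- Late onset only, among patients free of early ADA: 1.51/75.34 = 2.0% against 6.25/312.66 = 2.0%, ratio 1.00.

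| r | Up-titrated | Others | Unsplit ratio |
|---|---|---|---|
| 1 | 4.94% | 4.94% | 1.00 |
| 1.5 | 6.34% | 4.59% | 1.38 |
| 2 | 7.71% | 4.25% | 1.81 |

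The wider grid took u = 10%, 20% and 40%, with (e, l) = (2%, 3%), (3%, 2%) and (5%, 5%). The unsplit ratio ran from 1.22 to 2.49 for r of 1.5 to 2, and was 1.00 throughout for r = 1. Even with r = 1, about 40% to 61% of the up-titrated row's cases had arisen on 75 mg. The split ratio is 1.00 in every case, as it must be when no dose effect is assumed.

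**The case against.** The strongest reply is that SAP 2.4.7 describes patients and does not estimate a dose effect. A reader might infer that the plan attributes early antibodies to a 150 mg group. The text does not support that: the column is up-titration status, and SAP 2.4.8 says by dose when it means dose. The incidence item also splits pre-existing ADA by the same status, which no later dose could cause. This stands against any claim of explicit misattribution. It does not remove the problem, because SAP 2.4.5 treats the same status split as a per-dose description and protects it. If the aim was instead to see whether antibodies precede up-titration, positives after Week 12 blur that question, so the time split helps on either reading.

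Second, much is already visible. The by-time-point tables show Week 4 and Week 12 positivity separately, and an onset at either visit plainly precedes 150 mg. This stands for those tables, which need no change. They give positivity per visit, however, and not patient-level incidence or persistence.

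Third, a reader might infer that patients who stop treatment before Week 12, all of whom fall in the not-up-titrated column, give fewer ADA samples and so dilute it. Protocol 10.3.4 does not support this: those patients are to keep all remaining visits and attend an extra visit with end-of-treatment assessments, which include ADA. Only patients who leave the study would give fewer samples.

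Fourth, the size rests on assumption, and with no link between early ADA and up-titration the ratio is 1.0. This stands.

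**Conclusion.** The gap is real but limited. Three patient-level ADA tables use a status fixed at Week 12 to classify responses that may have been detected earlier, and the SAP's own safeguard in 2.4.5 is not carried over. A difference between the rows could therefore arise without any effect of 150 mg.

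Its size cannot be stated from the documents. Under the assumed rates, the unsplit ratio is 1.0 if early ADA does not affect up-titration and 1.22 to 2.49 if it raises the chance of up-titration 1.5- to 2-fold. These values show the mechanism and do not predict the result. The tables are descriptive, no primary or key secondary test is touched, and the by-arm tables still serve the ADA objective.

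Splitting by time of first detection removes the timing error. It does not make the later comparison randomized: SAP 2.4.5 itself expects up-titrated patients and those remaining on 75 mg to differ at baseline.

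**What to change.** In SAP 2.4.7, split treatment-emergent ADA incidence and time to onset by when the response was first detected:

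- **(a) Up to the first injection after the Week 12 transaction:** report for the alirocumab arm as a whole, labelled as arising on 75 mg. It may also be shown by later up-titration status, which would show whether early ADA precedes up-titration.
- **(b) After that injection:** report by up-titration status, among patients with a Week 12 transaction, a later injection, no earlier treatment-emergent ADA and at least one later ADA sample.

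Report persistent, transient and indeterminate classes for the whole alirocumab arm only. A post-Week-12 column by status would contain no persistent responses on planned visits, because Weeks 24 and 32 are less than 12 weeks apart. Leave the by-arm and by-time-point tables unchanged.

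The cost is a short addition to the SAP text, a few extra table rows and smaller counts per status. No new data are needed.
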